Randomization will be stratified by high-intensity statin (Yes/No) and HeFH (Yes/No) at baseline. High-intensity statin is defined as rosuvastatin 20 mg or 40 mg daily, atorvastatin 40 mg or 80 mg daily, or simvastatin 80 mg daily (if already on this dose for >1 year). To ensure an adequate number of patients with HeFH are included in this study and exposed to each dose, randomization will be stratified 2:1 (HeFH:non-HeFH; 24:12) within each treatment group.

Investigational medicinal product (IMP) administration during the double-blind treatment period will take place at the site and possibly, by visiting home nurses (only for the SC group). The IMP will be administered at the site on the day of randomization, after all samples for clinical laboratory evaluation have been obtained. In order to ease burden for those patients randomized to receive SC IMP, visiting home nurses may be utilized to administer SC IMP on odd visit dates, eg. Week 1, week 3, and week 5.

Open-Label Treatment Period (Group B only)

Patients in Group B (the IV treatment groups) will enter a 48-week open-label treatment period and all patients will receive evinacumab 15 mg/kg IV Q4W.

Follow-Up Period (Groups A and B)

All patients will be followed for 24 weeks after the last dose of study drug.

Patients should maintain their stable background LMT regimen from screening through the end of study (EOS) visit.

Patients will be reminded to adhere to a heart-healthy diet at screening, and continuing through the EOS visit. Patients should maintain a stable exercise level for the duration of the study, and avoid rigorous exercise 24 hours before each study visit. All lipid results will be blinded from after randomization until the week 36 visit for the IV cohorts, and until database lock for the SC cohorts.

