6. SELECTION, WITHDRAWAL, AND REPLACEMENT OF PATIENTS

6.1. Number of Patients Planned

Approximately 252 patients, at approximately 80 sites in the US and globally, will be randomized within either Group A (evinacumab 300 mg SC QW: evinacumab 300 mg SC Q2W: evinacumab 450 mg SC QW: placebo SC) or Group B (evinacumab 5 mg/kg IV Q4W: evinacumab 15 mg/kg IV Q4W: placebo IV). There will be 144 patients randomized to Group A (36 patients per treatment group), with 108 patients exposed to SC evinacumab and 36 exposed to SC placebo. There will be 108 patients randomized to Group B (36 patients per treatment group), with 72 patients exposed to IV evinacumab and 36 exposed to IV placebo.

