10.2. Justification of Sample Size

Four pairwise comparisons of evinacumab to a placebo control arm corresponding to the route of administration (Group A or Group B) are hypothesized for the primary efficacy analysis of this study. A total of 216 patients are planned for assessing the primary measure at week 16. Specifically, a sample size of 36 patients per treatment arm will have 90% power to detect a treatment group difference in mean percent change LDL-C of 20% in any 1 pairwise comparison (ie, evinacumab mean = 27% and control mean = 7%), assuming that the common standard deviation (SD) is 25 using an independent group t-test. This sample size has been adjusted for a 5% dropout rate. The alpha level for each of the 4 pairwise comparisons is 0.05 (2-sided), and assumes control of the overall type-1 error rate using a pre-specified hierarchical inferential approach.

Further, the evinacumab 5 mg/kg IV Q4W regimen has been added to Group B, allowing for an assessment of dose-response in the IV route of administration. The additional 36 patients for this second IV dose regimen culminate in a total of 252 patients planned for the study.

With the intent to gain evinacumab experience across these dose regimens for future study planning in patients with HeFH, a subgroup analysis is planned for the stratified sub-population of patients diagnosed with HeFH. To ensure an adequate number of patients are randomized into the HeFH strata level, a total of 175 patients are planned for assessing the percent change LDL-C from baseline at week 16. Specifically, a sample size of 36 patients per treatment arm will have 90% power to detect a treatment group difference in mean percent change LDL-C of 20% in any 1 pairwise comparison (ie, evinacumab mean = 27% and Control mean = 7%), assuming that the common SD is 20 using an independent group t-test. This sample size has been adjusted for a 5% dropout rate.

Blinded Sample Size Adjustment

Referencing the ICH E9 regulatory guidance, the study sample size may be re-estimated after approximately 75% of the patients reach the week 8 visit in the double-blind period, to ensure adequate power in the case of a larger-than-expected variability in the data. This sample size

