1.2.3. Modifications from the Statistical Section in the Final Protocol

The summary of modifications is listed in the following table.

Item	Protocol Section	Description
1	10.3.1.1 Intent-to-Treat (ITT)	SAP Section 3.1.1 Evaluable primary endpoint requirement for the primary analysis population was removed per FDA request.
2	10.3.2.1 Double-Blind Safety Analysis Set/second item “For patients receiving study drug from more than 1 treatment group during the trial, the treatment group allocation for as-treated analysis will be the one in which the patient was treated with the highest number of injections (Group A) or infusions (Group B).”	SAP Section 3.2: The second item for determining the as-treated treatment group will be conservatively changed to: “For randomized patients receiving both evinacumab and placebo study treatment during the trial, the treatment group allocation for as-treated analysis will be evinacumab.
3	10.4.3.1 Primary Efficacy Analysis “Each model will include the fixed categorical effects of treatment group (placebo and evinacumab dose regimens), randomization strata, time point (weeks 4, 8, 12, 16 for the Group B treatment groups; weeks 2, 4, 6, 8, 12, 16 for the Group A treatment groups)”	SAP Section 5.7.1 Timepoints in the MMRM model are updated: “Each model will include the fixed categorical effects of treatment group (evinacumab dose regimens versus placebo), randomization strata (high-intensity statin [Yes/No] and HeFH status

Item	Protocol Section	Description
		[Yes/No]), time point (weeks 2, 4, 6, 8, 12, 16 for the Group B treatment groups; weeks 2, 4, 6, 8, 10, 12, 14, 16 for the Group A treatment groups)”
4	4.2.2. Secondary Efficacy Analysis 
 • Proportion of patients with calculated LDL-C < 100 mg/dL (2.59 mmol/L) at week 16 • Proportion of patients with calculated LDL-C < 70 mg/dL (1.81 mmol/L) at week 16 	SAP Section 4.7.2 These two secondary endpoints were removed due to the protocol amendment for changes to the inclusion criteria. Specifically, the LDL-C threshold was lowered to aid patient enrollment, potentially allowing patients to achieve one or both of the secondary endpoints at baseline.

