3.2. Double-Blind Safety Analysis Set

The double-blind safety analysis set (SAF) considered for safety analyses will be the randomized population who received at least 1 dose or part of a dose of double-blind study drug. Patients will be analyzed according to the treatment received (placebo IV, evinacumab 5 mg/kg or 15 mg/kg IV Q4W, placebo SC, evinacumab 300 mg SC QW or Q2W, evinacumab 450 mg SC QW). Actual treatment received is defined as follows:

- For Group A, each study drug administration visit is assigned 3 kits with 150 mg IP concentration in each kit, and each kit contains either evinacumab or placebo. Different combinations of evinacumab or placebo kits determine the actual dosage as follows:
 - For the evinacumab 450 mg SC QW treatment group, the 3 kits at all weekly visits contain evinacumab as recorded in eCRF “Study Drug Administration- Evinacumab/Placebo SC”
 - For the 300 evinacumab mg SC QW treatment group, 2 kits contain evinacumab and 1 kit contains placebo at all weekly visits as recorded in eCRF “Study Drug Administration- Evinacumab/Placebo SC”
 - For the 300 evinacumab mg SC Q2W treatment group, 2 kits contain evinacumab and 1 kit contains placebo at all even-numbered weekly visits (Day 1, Week 2, Week 4, etc.) as recorded in eCRF “Study Drug Administration- Evinacumab/Placebo SC.” All odd-numbered weekly visits (Week 1, Week 3, etc.) contain 3 kits of placebo as recorded in eCRF “Study Drug Administration- Evinacumab/Placebo SC”
 - For the placebo SC QW treatment group, the 3 kits at all weekly visits contain placebo as recorded in eCRF “Study Drug Administration- Evinacumab/Placebo SC”
- For Group B, each study drug administration visit is assigned 1 kit, and it contains either evinacumab or placebo (regardless of evinacumab dose). The actual study

treatment received (placebo, evinacumab 5mg/kg IV, or evinacumab 15 mg/kg IV) is defined as follows:

- Active study treatment (evinacumab or placebo) is defined from the kit number in eCRF “Study Drug Administration- IV”
- Evinacumab study treatment dose (5 mg/kg or 15 mg/kg) is defined as “active study treatment = evinacumab” and the dose is defined in the “Total IP Dose Administration – IV Double-blind (Unblinded)” eCRF page.

In addition:

- Randomized patients for whom it is unclear whether they took the study drug will be included in the safety population as randomized.

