- For randomized patients receiving both evinacumab and placebo study treatment during the trial, the treatment group allocation for as-treated analysis will be evinacumab.
- If a randomized patient receives both evinacumab doses (300 mg SC and 450 mg SC for Group A; 5 mg/kg IV and 15 mg/kg IV for Group B), the treatment group allocation for as-treated analysis will be the most frequently administered evinacumab dose.

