4.8.1. Adverse Events Variables

The period of safety observation starts from the time when the patient gives informed consent and continues into the following periods:

- The PRE-TREATMENT period is defined from the day the ICF is signed to the day before the first dose of double-blind study treatment administration.
- The double-blind treatment-emergent adverse event (TEAE) period is defined from the day of the first dose of double-blind study treatment administration to the day of the last dose of double-blind study treatment administration + 168 days (24 weeks) (based on PK considerations, residual effect of study treatment might be observed until 24 weeks after the last dose of study drug) for those patients not proceeding into the OLTP (ie, Group A patients and Group B patients who prematurely discontinue study treatment), or up to the day before the first dose of open-label study treatment administration for those patients proceeding into the OLTP
- The open-label treatment-emergent adverse event (TEAE) period (Group B only) is defined from the day of the first open-label study treatment administration to the day of the last open-label study treatment administration + 168 days (24 weeks).
- The POST-TREATMENT period is defined from the day after the end of the respective TEAE periods to the last study visit.

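### The as-treated rules for the double-blind safety set are not limited to double-blind treatment, so read literally they reclassify IV placebo and 5 mg/kg patients by their later open-label drug

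*SAP*

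**What the plan says.** SAP 3.2 defines the double-blind safety set by receipt of at least part of a dose of double-blind drug and assigns columns as treated: "Patients will be analyzed according to the treatment received (placebo IV, evinacumab 5 mg/kg or 15 mg/kg IV Q4W, placebo SC", followed by the SC evinacumab arms. Two rules then deal with mixed exposure:

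- Placebo and evinacumab: "For randomized patients receiving both evinacumab and placebo study treatment during the trial, the treatment group allocation for as-treated analysis will be evinacumab".
- Two evinacumab doses: "the treatment group allocation for as-treated analysis will be the most frequently administered evinacumab dose". For Group B the doses named are 5 and 15 mg/kg IV.

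SAP 1.2.3, item 2, records the first rule as a change from Protocol 10.3.2.1: "The second item for determining the as-treated treatment group will be conservatively changed to" the present text. The protocol rule allocated by the highest number of injections or infusions. It too counted over the whole trial.

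Protocol 5.1 says that Group B patients "will enter a 48-week open-label treatment period and all patients will receive evinacumab 15 mg/kg IV Q4W". Protocol 6.1 plans Group B "with 72 patients exposed to IV evinacumab and 36 exposed to IV placebo".

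For patients who continue, SAP 4.8.1 closes the double-blind adverse-event period early, running it only "up to the day before the first dose of open-label study treatment administration for those patients proceeding into the OLTP".

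**The concern.** The first rule counts exposure over the whole trial and the second names no period, yet both decide the columns of double-blind tables. Crossing to evinacumab is the design for IV placebo patients, not an accident of dispensing. A programmer who follows the first rule to the letter would therefore move an IV placebo patient to evinacumab after one open-label infusion.

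The concurrent IV placebo group is the only IV comparator for adverse events, AESIs, laboratory values, vital signs and ECGs. SAP 5.8 presents double-blind safety with the evinacumab regimens pooled within each route, supported by the individual regimens and placebo. Moving placebo patients would shrink the comparator and add events that occurred on placebo to the evinacumab column. Moving 5 mg/kg patients would blur the dose comparison.

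**Working it through.** **Planned columns.** Protocol 10.2 uses a difference of 20 points, SD 25, two-sided alpha 0.05 and 90% power with a two-sample t-test. With n = 34 per arm the noncentrality is 20 / (25 × √(2/34)) = 3.30 on 66 degrees of freedom, and power is 0.9015. Allowing for dropout ("This sample size has been adjusted for a 5% dropout rate"), 34 / 0.95 = 35.8, which rounds up to 36. This reproduces the plan. Group B is 3 × 36 = 108: 36 placebo and 72 evinacumab.

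**First rule, read literally.** The SAP calls open-label drug study treatment, and the first open-label infusion is scheduled at week 24 (Protocol Table 4). The number moved is 36 × (1 − d), where d is the share of placebo patients who never start open-label drug. The documents do not give d. The 5% row borrows the sample-size dropout as a proxy; the other rows are assumptions.

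| d | Placebo patients moved | Left in placebo column | Pooled evinacumab column | Share of that column with no double-blind evinacumab |
|---|---|---|---|---|
| 0% | 36.0 | 0.0 | 108.0 | 33.3% |
| 5% | 34.2 | 1.8 | 106.2 | 32.2% |
| 10% | 32.4 | 3.6 | 104.4 | 31.0% |
| 20% | 28.8 | 7.2 | 100.8 | 28.6% |

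**Effect on a signal (illustration).** Assume true event rates of 20% on evinacumab and 10% on placebo. At d = 5% the pooled column shows (72 × 0.20 + 34.2 × 0.10) / 106.2 = 17.82 / 106.2 = 16.8%, beside a comparator of about 2 patients. The rule is described as conservative, but here it would dilute the signal.

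**Second rule, read literally.** Protocol Tables 4 and 5 schedule 6 double-blind infusions (weeks 0, 4, 8, 12, 16, 20) and 12 open-label infusions (every 4 weeks from week 24 to week 68). A 5 mg/kg completer ends with 6 infusions at 5 mg/kg and 12 at 15 mg/kg. The rule then returns 15 mg/kg. The count ties at the sixth open-label infusion and turns at the seventh, scheduled at week 48, so the effect is complete by the final analysis.

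**Timing.** The first-step analysis uses Group B data through week 24 (SAP 7.1). The first rule needs only one open-label infusion, scheduled at that same visit, so the data cut does not prevent the problem.

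**What is not touched.** ITT and mITT are analysed as randomized (SAP 3.1.1 and 3.1.2). Group A has no open-label period in this trial. The alternating placebo in its Q2W arm is part of that regimen, so classing those patients as evinacumab is right.

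**With the period limited.** The planned double-blind IV columns return to 36 placebo and 72 evinacumab (36 + 36), and only genuine kit errors are reallocated.

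**The case against.** The strongest reply is that the context already supplies the limit, and as evidence of intent this stands. The rules sit under a double-blind heading, in a set defined by double-blind drug, with placebo IV listed as a column. The Group B dose is read from an eCRF page labelled double-blind. Open-label exposure has its own set (SAP 3.3). The adverse-event cut-off in SAP 4.8.1 and the open-label tables in SAP 5.8, which are split by double-blind treatment including placebo, make sense only if placebo patients stay placebo patients. On this view the rules are tie-breakers for dispensing errors. But none of these passages limits the rules themselves, and several conflict with their wording.

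A reader might also infer that the SAP's change to the rule created the problem. The documents do not support that. The trial-wide time frame was already in Protocol 10.3.2.1. Read just as literally, the protocol's highest-count rule would also move placebo completers (6 placebo infusions against 12 of evinacumab). The SAP change lowered the trigger to a single infusion, and SAP 1.2.3 shows no decision about the time frame.

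Nor does the second rule fail to place a crossed-over placebo patient. Such a patient has had only one evinacumab dose, 15 mg/kg, so that rule does not apply. What is unclear is whether the patient would enter the 15 mg/kg column or only the pooled one, because the double-blind dose page holds no evinacumab dose for them.

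Finally, the safety analysis is descriptive with no formal testing, so no error rate is at stake. That is true, but the first-step results may go to health authorities (SAP 7.1).

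**Conclusion.** This is a wording error in an operative rule, and it conflicts with the rest of the SAP. Followed to the letter, it would move 29 to 36 of the 36 planned IV placebo patients into the evinacumab column, leaving 0 to 7. It would also move 5 mg/kg completers to 15 mg/kg in any double-blind table produced at the final analysis. The range rests on an assumed 0 to 20% not continuing; a figure such as 34 of 36 is arithmetic on a borrowed dropout rate, not a forecast.

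A reader might go further and conclude that the IV placebo comparator will disappear, or that the sponsor means it to. The documents do not support this, because the surrounding sections consistently point to double-blind treatment only. The point is that a rule fixed before unblinding should not depend on the programmer inferring its limit.

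**What to change.** In SAP 3.2, limit both mixed-exposure rules to study treatment received during the double-blind treatment period, and make the same change in item 2 of SAP 1.2.3. Changing only the first rule would leave the 5 mg/kg patients exposed to the same problem.

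It is safest to write *double-blind study treatment received during the double-blind treatment period*. SAP 5.8.3 lets that period run up to the day of the first open-label infusion, so a period limit alone could be read to include that infusion.

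The cost is a few words in a SAP revision before the first-step database lock. No new data and no change to the design or the efficacy analyses are needed.

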3.3. Open-Label Safety Analysis Set

For Group B, the open-label SAF considered for safety analyses will be the randomized population who received at least 1 dose or part of a dose of open-label study drug.

3.4. Pharmacokinetic (PK) Analysis Set

The PK analysis set is defined as all randomized patients who received any study drug and have at least 1 non-missing post-baseline measurement of evinacumab concentration. Treatment assignments for the DBTP are based on the treatment received (placebo or evinacumab).

The total target analysis set is defined as all randomized patients who received any study drug and have at least 1 non-missing measurement of total ANGPTL3 concentration following the first dose of study drug.

3.5. The Immunogenicity Analysis Set

The anti-evinacumab antibody (ADA) analysis set is defined as all randomized patients who received any study treatment, and have at least 1 non-missing ADA result following the first dose of study treatment. Patients will be analyzed according to a treatment actually received.

The neutralizing antibody (NAb) analysis set includes all subjects/patients who received any study drug and who are negative in the REGN1500 ADA assay or with at least one non-missing result in the REGN1500 NAb assay after first dose of the study drug. Patients who are ADA negative are set to negative in the NAb analysis set. Patients will be analyzed according to the treatment actually received.

3.6. Pharmacodynamic (PD) Analysis Set

The PD population includes all treated patients who received any study drug (safety population) and had at least one non-missing protocol defined PD marker (as defined in Protocol/Section 8.2.5) following the first dose of study drug.

4. ANALYSIS VARIABLES

4.1. Demographic and Baseline Characteristics

For each patient, demographic and baseline characteristics will be obtained from the last available value up to the date of the first study treatment administration (i.e. baseline definition). For patients randomized and not treated in R1500-CL-1643, the baseline value is defined as the last available measurement prior to the date of randomization.

All baseline safety and efficacy parameters (apart from those listed below) will be presented along with the summary statistics in the safety and efficacy sections.

The following variables will be summarized:

Demographic Characteristics

- Sex (Male, Female)
- Race (White, Black or African American, Asian, American Indian or Alaska Native, Native Hawaiian or other Pacific Islander, Not Reported, Other)
- Age in years (quantitative and qualitative variable: ≥ 18 to < 45 , ≥ 45 to < 65 , ≥ 65 to < 75 , and ≥ 75 years; and < 65 , and ≥ 65 years)
- Ethnicity (Hispanic or Latino, Not Hispanic or Latino, Not reported, Unknown)

Baseline Characteristics

- Baseline Weight (kg)
- Baseline Height (cm)
- Baseline Body mass index (BMI) in kg/m^2 (quantitative and qualitative variable defined as < 30 , ≥ 30)
- Smoking Status (never, former, and current smoker)
- Current alcohol consumption (yes/no)
- Randomization strata as reported in the IVRS
 - High intensity statin (Yes/No)
 - HeFH status (Yes/ No)
- Randomization strata as reported from the e-CRF

Baseline Disease Characteristics

- Lipid parameters - quantitative variables for all efficacy parameters

- HbA1c both quantitative variable and qualitative variable defined as: <5.7%, ≥5.7% to <6.5%, ≥6.5%
- hs-CRP
- Calculated LDL-C categories: <70, ≥ 70 to <100, ≥100 to <130, ≥130 to <160, ≥160 to <190, ≥190 mg/dL (<1.81, ≥1.81, <2.59, ≥2.59 to <3.37, ≥3.37 to <4.14, ≥4.14 to <4.91, ≥4.91 mmol/L)
- Fasting TG categories: <150, ≥150 to <200, ≥200 mg/dL, and category ≥150 mg/dL for mixed dyslipidemia (<1.7, ≥1.7 to <2.3, ≥2.3 mmol/L, and category ≥ 1.7 mmol/L),
- Lp(a) categories: <30, ≥30 to <50, ≥50 mg/dL, and category ≥30 mg/dL (<75, ≥75 to <125, and ≥125 nmol/L, and category ≥ 75 nmol/L)

4.2. Medical History

As applicable, patient medical history, pre-listed or not in the e-CRF will be dictionary coded by primary system organ class and preferred term using the Medical Dictionary for Regulatory Activities (MedDRA), specifically the MedDRA version in effect at the time of the first database lock. The medical history of interest collected on dedicated and pre-listed e-CRFs is: cardiovascular history and risk factors, Primary and secondary CVD prevention, CV risk factors categorized by high and very high risk, hypercholesterolemia disease history (including LMT therapies) are also defined below from pre-defined risk factors collected on e-CRF.

Medical history of interest is defined as the occurrence of these diseases:

1. Coronary heart disease (CHD)
2. CHD risk equivalents
3. Cardiovascular (CV) risk factors other than hypercholesterolemia (hypertension, type 2 diabetes, type 1 diabetes, family history of premature CHD).
4. Family history of type 2 diabetes

CHD and CHD risk equivalents will be derived from the respective e-CRF as follows:

1. Coronary heart disease (CHD) (regardless if it is ongoing or not) is defined as the occurrence of at least one of the following events:
 - Acute myocardial infarction
 - Silent myocardial infarction
 - Angina (chronic stable or unstable)
 - Coronary revascularization procedure (e.g. PCI, CABG)
2. CHD risk equivalent (regardless if it is ongoing or not) is defined as the occurrence of at least one of the following events:
 - Peripheral arterial disease (PAD)
 - Ischemic stroke

- Chronic kidney disease (CKD)
- Known history of diabetes mellitus (type 1 or 2) AND 2 or more additional risk factors among:
 - History of ankle-brachial index ≤ 0.90
 - History of hypertension
 - History of microalbuminuria or macroalbuminuria
 - History of proliferative diabetic retinopathy
 - Known family history of premature CHD

Secondary CVD prevention is defined as patients with any of the following history of CVD (other patients will be classified as primary CVD prevention):

- History of CHD (as defined above)
- History of ischemic stroke
- History of PAD with severity criteria defined as one of the following events:
 - PAD and ankle brachial index ≤ 0.90
 - Peripheral revascularization procedure (angioplasty, stenting) for PAD
 - Thrombolysis for PAD
 - Peripheral revascularization surgery (arterial bypass) for PAD

CV Risk Factors are defined for this study as high risk and very high risk below.

- Very high CV risk patients are defined as patients with CHD or CHD risk equivalents.
- High CV risk patients are defined as all other patients.

Hypercholesterolemia disease history will be assessed through diagnosis of HeFH, time from diagnosis to study randomization (years), method of diagnosis of HeFH (genotyping, clinical diagnosis), lipid modifying therapies history reported in the “History of Hypercholesterolemia /Statin Use” e-CRF page.

